Overview of Study Data Collection: To achieve all aims, we will conduct a cluster-randomized stepped wedge study across three representative clusters (each containing a district center and two rural sites) in the Kedougou region. For each aim we will collect data at baseline and at 6-month intervals in each cluster (data collection intervals coincide with the initiation of the intervention in a new cluster). In aim 1, we will develop (through a participatory approach), pilot, and conduct surveys and interviews of eligible clients as well as focus groups (FG) (women ages 30-44 and 45-59) and interviews of men (ages 30-59). For aim 2, we will describe the development, piloting, implementation, and adaptation of an aim 1-informed context-specific multi-level peer education curriculum across clusters through the stepped wedge approach^{59,60} in the Kedougou region. We will collect quantitative program reach data and qualitative process evaluation data at each time period. These data will be used to adapt the intervention over time. To achieve aim 3, we will collect aggregated health service level utilization data and individual surveys.

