3.0 Research Goals and Aims

BROAD GOALS OF THE RESEARCH

The goal of this study is to strengthen the **implementation** of a cervical cancer screening service in a decentralized, low-resource area of Senegal naïve to any cancer screening programs by investigating the barriers and facilitators of **initial uptake** and developing and adapting a peer education health promotion intervention to diverse and dynamic contexts to achieve **sustained utilization**.

Through the **SPECIFIC AIMS**, we will

Aim 1: Assess cervical cancer screening access determinants in Kedougou, Senegal by identifying barriers and facilitators of service uptake over time at the person, household, and community levels;

Aim 2: Develop and deploy a wide-reaching, multi-level responsive peer education curriculum aimed at motivating eligible women to seek cervical cancer screenings in Kedougou, Senegal;

Hypothesis: A cervical cancer peer education curriculum developed, implemented, and adapted through a Care Group model will reach 75% of the target audience, improve cervical cancer knowledge, and establish the rate of women and men recommending this screening service to others to 30% over the course of 24 months in the region of Kedougou, Senegal; and

Aim 3: Evaluate the impact of the peer education intervention on initial screening uptake and re-screening rates.

Hypothesis: A context-specific peer education cervical cancer screening curriculum will increase the cervical cancer screening initial uptake rate (first 6 months) in target age women to 35% and will ensure 2 year re-screening rates of 30% in the Kedougou, Senegal study sites.

STUDY DESIGN AND PROCEDURES

[figure not shown]
TABLE 1: Primary Research Questions

AIM	Research Questions
AIM 1	What individual, household, and community factors influence a woman's decision to seek or not to seek cervical cancer screening in Kedougou, Senegal? How do these identified determinants change with time? How does age and gender specifically influence screening program opinions and motivations for screening?
AIM 2	What is the structure, process, and content of a peer education program that empowers eligible women to initially seek cervical cancer screening services in Kedougou, Senegal? What programmatic factors predict the reach and positive reception by a relevant audience of such a health promotion intervention?

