AIM 3	How does a peer education program impact the cervical cancer screening service initial uptake by eligible women seeking a first-time screening and ensure sustained utilization and continuing impact of the cervical cancer screening service?

Study Design: Figure 2 is a schematic example for this trial design. In this example, Cluster 1 (randomly selected) crosses to the intervention arm at Period 2, Cluster 2 (randomly selected) crosses over to the intervention arm at Period 3, and so on. By the end of the study, all clusters will cross over to the intervention arm (one-way), though in random order. At the end of the final time period, the outcome of interest is compared between the intervention and control periods within each cluster. Differences in service utilization and recommendation will be compared, whereby clusters serve as their own controls as they cross over from the control to intervention group.

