Detailed Care Group Focus Group Sampling: At the beginning of a Care Group Meeting, the RA will explain that she will be conducting a short focus group. The RA will read the FOCUS GROUP RECRUITMENT SCRIPT and ask for interest to participate. The RA will invite all present members of the Care Group who express interest to participate in a focus group. The RA will read the INFORMED CONSENT and SHORT FORM to each of the chosen participants separately. The RA will obtain participant written consent with the SHORT FORM, separately and privately, and will invite them into the private focus group area and introduce them to the observers.

Aim 3: Evaluate the impact of the intervention on initial screening uptake and re-screening rates. (See Table 4)

TABLE 4: Aim 3 - Initial & Sustained Change Data Collection

Methodology			Measures	Variables
Quantitative	g Document Review DCI: 1612	No human participants. Review of aggregated health service records.	Initial Uptake/ Sustained utilization	
A. Number/% of women screened for the first time, age stratified 1
 
B. Number/% of women being re-screened, age stratified
 
C. Number/% of positive screened women referred/treated (aggregated data only)

	a Individual Interval Interview DCI: 1603, 1604	Systematic sampled individuals followed over time. Sample size: n = 0 new of sample a		

To achieve aim 3, we will follow cluster-wide trends through aggregated health service data⁶⁹ and participant-level impact through individual interviews. **Health service data** (# of initial and re-screenings stratified by age and number of referred women who completed treatment) will be reported by each cluster to the district center through the standard reporting structure. These de-identified data are reported to the regional level where they will be collected. Through the individual interviews described in aim 1 above (Table 2), we will collect impact data within our participant population in the form of first-time and re-screenings.

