
Mixed methods Analysis and Writing. Mixed methods involves integrating the multiple types of data using well-accepted designs including: triangulation, explanation, transformation, and exploration.⁷⁵ We will use both SAS and Atlas/ti to further analyze data that will have already been collected, coded, and analyzed. Key to this integrated analysis is looking for intersections across levels that may explain: **1)** Which access facilitators best address barriers to seeking cervical cancer screening services among women who are most at risk? **2)** What benefits do interventions at each level of intervention (individual, household, or community) provide? **3)** What role does gender or age play in affecting barriers to accessing screening? **4)** What are the most influential sources that change motivation of screening eligible women change over time? **5)** What will most likely predict

that screening eligible women recommend screening to their peers? The analyzed data will be used to generate mixed methods publications responding to these key themes and will add to the body of knowledge for improving initial uptake and sustained utilization of cervical cancer screening services.

Power calculations

Clusters and Population: There will be three clusters comprising separate districts (Kedougou, Salemata, and Saraya) in Kedougou. Using two independent proportion method of cluster randomization power analysis (PASS13), to obtain the power 80% under significance level 0.05, the 10% difference of the screening rate with assumed ICC 0.01 requires n=15 per each of 3 clusters. Tables 2, 3, and 4 outline the data collection methodology for each aim. These data will be collected within each cluster at baseline and every six months - coinciding with a crossover of a new (random) cluster. Our selected sites are comprised of zones representative of region including rural, district center, semi-urban, and urban. Contamination is unlikely given distance (the distance between sites ranges from 32 kilometers / 45 minutes by car to 3 ½ hours by car).

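### Aim 3 claims an impact on 2-year re-screening, but no woman first screened in the trial can complete a 2-year interval under control

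*Protocol*

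**What the plan says.** Section 3.0 states Aim 3 as "Evaluate the impact of the peer education intervention on initial screening uptake and re-screening rates". The hypothesis beneath it says that the curriculum will raise first-time uptake in the first 6 months to 35% and "will ensure 2 year re-screening rates of 30% in the Kedougou, Senegal study sites". No control rate is given for re-screening.

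The comparison is set out under Study Design in the same section: "At the end of the final time period, the outcome of interest is compared between the intervention and control periods within each cluster". Each cluster acts as its own control, all clusters cross one way, and service utilization is named among the things compared.

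The schedule appears in three places. Section 2.0 says "we will conduct a cluster-randomized stepped wedge study across three representative clusters" and that "data collection intervals coincide with the initiation of the intervention in a new cluster". Section 6.0 (Power calculations) repeats it: "These data will be collected within each cluster at baseline and every six months - coinciding with a crossover of a new (random) cluster". The Study Design text, describing a figure that is not shown, has a first cluster that "crosses to the intervention arm at Period 2, Cluster 2 (randomly selected) crosses over to the intervention arm at Period 3, and so on".

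Re-screening data come from two sources (section 3.0, Table 4 and the text below it). One is the individual interval interview. The other is aggregated health-service counts, of which the protocol says "These de-identified data are reported to the regional level where they will be collected".

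**The concern.** The aim and hypothesis use causal language for an outcome that takes 24 months to mature. The design compares control time with intervention time, and its control periods are much shorter than 24 months. If the women whose 2-year re-screening is measured were first screened during the trial, the control side of the comparison is empty.

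Two misreadings are then at stake. An observed 30% could be credited to peer education with no rate to set it against. Or a control rate could be built from women screened before the study and compared with an intervention rate built from women first screened in it, which mixes the effect of the programme with differences between two cohorts.

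**Working it through.** The protocol gives no control rate, sample size or power for re-screening; the calculation in section 6.0 concerns a difference in the screening rate. There is therefore no stated figure to reproduce. What can be checked is the timeline.

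**Inputs**
- Clusters: 3 (section 2.0).
- Step length: 6 months, one new cluster per step (sections 2.0 and 6.0).
- Crossovers: Periods 2 and 3, and by extension Period 4 (section 3.0, Study Design).
- End of data, L: month 36 from the 3-year study period. Section 3.0 (Aim 1) also says the interval interviews are done six times; six rounds starting at baseline end at month 30. Both are tried.

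**1. Control time.** The k-th cluster to cross has 6 × k months under control: 6, 12 and 18. If the first cluster crosses at baseline, the values are 0, 6 and 12.

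**2. Control side.** A woman first screened at month m ≥ 0 reaches 2 years at m + 24 ≥ 24. The longest control period is 18 months, and 24 > 18, so none of these intervals ends under control. If 2-year re-screening means re-screened at any time within 2 years, an early re-screen could fall in control time, but no 24-month window could be completed there. For the last cluster to exceed 24 control months, the step s would have to satisfy 3s > 24, so s > 8 months.

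**3. Intervention side.** A 2-year interval lying wholly under intervention needs a first screen with 6k ≤ m ≤ L − 24.

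| Cluster | Crossover (month) | First-screen window, L = 36 | First-screen window, L = 30 |
|---|---|---|---|
| 1 | 6 | 6 to 12 | month 6 only |
| 2 | 12 | month 12 only | none |
| 3 | 18 | none | none |

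With crossovers at months 0, 6 and 12 and L = 36, the windows are 0 to 12, 6 to 12 and month 12 only. The second cluster then contributes on the intervention side, but the control side stays empty.

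**4. Share of first screens.** Assume first screens spread evenly over time and clusters, with crossovers at 6, 12 and 18.
- L = 36 (3 × 36 = 108 cluster-months): wholly control 0. Starting under control and ending under intervention, (6 + 12 + 12)/108 = 28%. Wholly intervention, 6/108 = 6%. The rest do not reach 24 months.
- L = 30 (3 × 30 = 90 cluster-months): wholly control 0; mixed (6 + 6 + 6)/90 = 20%; wholly intervention about 0.

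**5. Women screened before the study.** They can reach 2 years during a control period. How many are in the interview cohort is not stated, so the following is illustrative only.
- At 5%, the 2014 campaign yield in section 1.0: 0.05 × 225 = 11 women, or 0.05 × 75 = about 4 per cluster.
- At the national participation figures in section 1.0: 0.019 × 225 = 4 and 0.069 × 225 = 16.
- Table 2 lists 45 women per cluster for the interval interview. On that base, 5% of 135 is about 7.

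**The case against.** The strongest reply is that the protocol does not confine re-screening to women first screened in the trial. Table 4 counts re-screened women by age group without limiting when they were first screened, and the service predates the study: section 1.0 reports 509 women screened in 2014 alone. Re-screens can therefore occur in control periods. A reader might infer that no effect on re-screening can be estimated at all; the documents do not support that.

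It can also be said that the 2-year figure appears only in the hypothesis, as a level to reach, while the Study Design text speaks of an outcome of interest and of service utilization in general. On that reading, per-period re-screening is compared between conditions and the 30% is a separate target. A reader might infer that the protocol expressly assigns 2-year re-screening to the within-cluster contrast; it does not go that far.

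Both points stand and limit the finding. They do not remove it. The protocol defines no re-screening denominator and does not say that earlier clients supply the control rate. Nor does it say that the aggregated, de-identified records show when a woman was last screened or how many women are due. The indicators are to be agreed at study start (section 5.0) and an analysis plan may define more, but no definition creates control time that the schedule excludes. And if 30% is only a target, the wording about ensuring it and evaluating impact claims more than a target can show.

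The counts in step 5 should carry little weight. The 5% is one year's campaign yield, not the share ever screened, and Care Group volunteers may not be typical. The counts also leave out the cluster-wide service records, where the pool of earlier clients is larger.

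**Conclusion.** The point holds for women first screened in the trial. None of their 2-year intervals can be completed under control, because the longest control period is 18 months (12 on the alternative schedule). Their 2-year re-screening rate has no control counterpart, so reaching 30% would not demonstrate impact. Even the intervention side is thin: about 6% of first screens with data to month 36, essentially all in the first cluster to cross, and about none with data to month 30.

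Re-screening in general is not ruled out as a comparison, since earlier clients may give a limited control rate. That would be a different cohort, of a size the protocol does not state.

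The conclusion rests on the 6-month step and the crossover order given in the text, because the design figure is not shown. The percentages also assume an even spread of first screens. The absence of control intervals does not depend on that.

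**What to change.** Reword Aim 3 and its hypothesis so that the impact claim covers initial uptake only. Report 2-year re-screening as a descriptive proportion with a confidence interval, among women whose first screen was at least 24 months earlier. Say that the 30% is a benchmark and not evidence of effect.

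If a re-screening comparison is still wanted, define one that exists in both conditions. Among women whose last screen, pre-study screens included, was 2 or more years before a period began, take the proportion screened in that 6-month period. Expect it to be imprecise if it rests on the interview cohort.

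Both versions need the interval interview to record screening dates: the first screen for the descriptive rate, the last screen for the comparison. Table 2 lists screening history but does not say that it is dated, so the sponsor should confirm this or add the item.

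The cost is protocol wording, one dated interview item if it is not already there, and giving up a causal claim on 2-year re-screening that the schedule cannot support.

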TABLE 2: Aim 1 - Demand-Side Access Data Collection

		Methodology	Measures	Variables
Quant	a	Individual Baseline Survey BL / End DCI: 1601, 1602	Systematic sampled individuals (Women: 75 / cluster) (Men: 30 / cluster) Sample size: n = 315	Demographics: # of people / roles in household, genders, # of eligible women, # of women seeking screening, health seeking decision making process / power, cost concern, facility proximity, health practices and opinions, knowledge and opinions of partners of eligible clients.
	b	Individual Interval Interview DCI: 1603, 1604	Systematic sampled individuals (Women: 45 / cluster) (Men: 30 / cluster of sample a)	Socio-demographics: Age, gender, marital type/status, education level Behavioral risk factors: Sexual debut, lifetime sexual partners, gravity, parity, age at first birth, number of children, smoking status, diet Clinical risk factors: History of STI, weight, long-term oral contraceptive use Health literacy / seeking: Cervical cancer screening history & knowledge, preventative care opinions, health service utilization
Qual	C	Women's Focus Groups DCI: 1605	Purposive-sampled groups (women, 30-44 or 45-59) of sample a	Demand-side access ref Instruments ⁴² Ability to perceive: Health literacy, Health beliefs, Trust and expectations Ability to seek: Personal and social values, culture, gender, autonomy Ability to reach: Living environments, Transport, Mobility, Social support Ability to pay: Income, Assets, Social capital, Health insurance Ability to engage: Empowerment, Information, Adherence, Caregiver support

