To achieve Aim 1, we will orient 3 CGs in each cluster. Through a participatory process involving CG leaders, health service leaders, midwives, and community members (women and men) we will develop, field test, and refine quantitative individual-level surveys that gather access barriers data corresponding to the variables listed in Table 2. We will conduct quantitative **a) Individual Baseline Surveys** with the same enrolled women (up to 25) and the same 10 men in each site per cluster. These data will be collected at baseline and at the end of the study period (after 3 years). We will also conduct **b) Individual Interval Interviews** with the same women (up to 25) and the same 10 men in each site per cluster. These data will be collected at baseline and every six months through the end of the study period (after 3 years). Therefore, these data will be collected six (6) times. These pre-tested, approved standard individual-level questionnaires (close ended) will be administered (face-to-face) by an RA of the same gender as the participant in the participants' preferred language (Malinke, Pulaar, or French). We will also conduct **c) Women's Focus Groups**. Through these FGs we will collect qualitative data, from women stratified by age, describing demand-side access barriers and facilitators (Table 2). The Research Assistant will moderate the 45 minute FGs in the preferred language (Malinke, Pulaar, or French) and two PCVs will observe and record written observations in real time. We will audio record the sessions (to be transcribed into both French and English). The Research Assistant and PCVs will review the audio record and confirm all notes. Below are described the recruitment and enrollment procedures for these data collection events.

Recruitment and Enrollment of Participants Followed within Households

We will utilize a random cluster sampling method to select ten (10) households in each of the three (3) sites per cluster. We will convenience sample one woman and one man in each of the households among those

who express a willingness to participate. We will ensure that the ten (10) chosen households fall within the households where the educational Care Group intervention takes place. Given that each Care Group will cover between 80 and 100 households, we are expecting to enroll participants from 10% of the households where the Care Group intervention occurs.

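### The 2-year re-screening claim for all study sites has no stated start point, and on the implied schedule the third cluster has only about 18 months after crossover

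*Protocol*

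**What the plan says.** The second half of the Aim 3 hypothesis (Protocol section 3.0) is that the curriculum "will ensure 2 year re-screening rates of 30% in the Kedougou, Senegal study sites". The first half sets a 35% initial uptake target for the first 6 months. Neither the hypothesis nor Table 4, which lists only the number and percentage of women re-screened by age, says from which event the 2 years run or which women form the denominator.

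The calendar is spread over several places:

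- Section 2.0 describes three clusters with six-monthly data collection, where "data collection intervals coincide with the initiation of the intervention in a new cluster". The power paragraph in section 6.0 repeats this.
- The Study Design paragraph in section 3.0 says "Figure 2 is a schematic example for this trial design". In that example Cluster 1 "crosses to the intervention arm at Period 2, Cluster 2 (randomly selected) crosses over to the intervention arm at Period 3", and so on. It adds that "the outcome of interest is compared between the intervention and control periods within each cluster".
- For the interval interviews, the Aim 1 procedures say: "These data will be collected at baseline and every six months through the end of the study period (after 3 years". The next sentence gives the number of rounds as six. Section 5.0 also refers to a three-year study.

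**The concern.** A 2-year rate needs 24 months of observation after its starting event. In a stepped wedge of fixed length, each later cluster has less time after crossover than the one before. A claim about all study sites therefore has to be checked against the last cluster to cross.

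Sustained use is half of the Aim 3 hypothesis and part of the study's stated goal. If the last cluster cannot reach 24 months, a figure given for all sites would in fact rest on one or two clusters. If women with shorter follow-up were kept in the denominator as not re-screened, the rate would be pulled down by an amount that depends on the randomised crossover order. An analysis plan can define the denominator and the censoring, but it cannot add follow-up time.

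**Working it through.** **Inputs.** Three clusters (section 2.0). One crossover per six-month interval (sections 2.0 and 6.0). First crossover at Period 2 (section 3.0, Study Design, given as an example). End of study at month 36 (section 3.0 Aim 1 procedures; section 5.0). Uptake window of 6 months (section 3.0, Aim 3 hypothesis).

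**Assumption.** Periods last six months and Period 1 starts at baseline. Crossovers *c* then fall at months 6, 12 and 18. The protocol prints no crossover month.

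**Formulas.**
- Follow-up from crossover = 36 − *c*.
- Follow-up for a woman first screened in the uptake window lies between 36 − (*c* + 6) and 36 − *c*.
- End month needed for everyone first screened in the window to have 24 months = *c* + 6 + 24 = *c* + 30.

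**Implied schedule (crossovers at months 6, 12, 18):**

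| Cluster by crossover order | *c* | From crossover | From first screen in window | End month needed (*c* + 30) |
|---|---|---|---|---|
| First | 6 | 30 months | 24-30 months | 36 |
| Second | 12 | 24 months | 18-24 months | 42 |
| Third | 18 | 18 months | 12-18 months | 48 |

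Counted from crossover, two of three clusters reach 24 months. Counted from a first screen in the window, only the first does so for all such women.

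**Most generous schedule (crossovers at months 0, 6, 12):** 36, 30 and 24 months from crossover, and 30-36, 24-30 and 18-24 months from a first screen in the window. All clusters now reach 24 months from crossover, but the third cluster's window still falls short.

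**No shift of start date removes the problem for women first screened in the window.** The third cluster would need *c* + 30 ≤ 36, that is *c* ≤ 6. With one crossover per six months, the third crossover cannot come before month 12.

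**Women first screened before crossover.** In the third cluster on the implied schedule, a woman first screened by month 12 reaches 24 months by month 36. At most 36 − 18 = 18 of those months fall under the intervention.

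**Interview rounds.** Months 0, 6, 12, 18, 24, 30 and 36 give 36/6 + 1 = 7 rounds. The stated six is not reproduced unless baseline is left out of the count.

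**The case against.** The strongest reply is that the 18-month figure is inferred. Figure 2 is called schematic, its cells are not available here, and period length is never stated separately from the data collection interval. This stands, and the figure should be read as implied. The alternative of crossovers at 0, 6 and 12 is not excluded. It fits the text poorly, because the first cluster would have no control period for the within-cluster comparison, and because the curriculum is to draw on Aim 1 findings and go only to clusters that have crossed over. It would also still leave the third cluster's uptake window short of 2 years.

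The second reply is that the hypothesis never says the 2 years begin at or after crossover. The screening service predates the trial (section 1.0 reports 509 women screened in 2014), and the interval interview collects screening history (Table 2). Women already screened could therefore be followed for 2 years in every cluster. This also stands. A reader might infer that no 2-year rate can be observed in the third cluster at all, and the documents do not support that. What they support is narrower: such a rate cannot be shown in all sites for women whom the intervention brings in.

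A reader might also infer from the count of six rounds that the month-36 interview will be dropped, shortening follow-up further. The text places a round at the end of three years, and six is equally the number of rounds after baseline. This is a counting inconsistency to reconcile, not evidence of lost follow-up. Nor does the protocol say that women with short follow-up will be counted as not re-screened; that is a risk to close off.

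Finally, Aim 3 also uses aggregated service records, which cover more women than the interviews. A verdict on precision from the interview sample alone would not describe them. They do share the three-year limit, and as de-identified aggregate counts they cannot tie a woman's first screen to her later one.

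**Conclusion.** The point holds in a limited form. The 2-year claim for all study sites is wrong as written for women first screened as a result of the intervention. On the implied schedule, two of three clusters reach 24 months from crossover, and one of three does so for everyone first screened in the 6-month window. That result rests on six-month periods, a first crossover at month 6 and an end at month 36. The shortfall for the third cluster's uptake window does not depend on the first-crossover assumption; it holds for any schedule with one crossover per six months inside 36 months.

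The start of the 2 years is undefined, and the answer depends on it. The matter is therefore one of defining and limiting a claim: worth changing, but modest in weight, and it does not touch the 6-month uptake half of the hypothesis. The interview round count is a separate, smaller inconsistency.

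**What to change.** 1. State the start event and the denominator of the 2-year rate, for example from a woman's first screen, among women screened at least once.
2. Limit the 30% figure to the cluster or clusters that can reach 24 months, and present it as a descriptive target.
3. Report the other clusters only to the horizon they reach. In the interview cohort, do this by cluster with censoring at the last interview, so that women with under two years are not counted as not re-screened.
4. Show women first screened before their cluster's crossover separately.
5. Keep the aggregated service counts as a descriptive measure of re-screening.
6. Print the crossover months, and correct the number of interview rounds to seven, or say that six excludes baseline. Make clear that the month-36 interview is held.

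The cost is wording, one analysis change and, if not already asked, a screening-date item in the interval interview. No sites or participants are added, and a round at the end of three years is already described. The downside is a narrower and less precise statement about sustained use. Keeping the claim for everyone first screened in the window at all sites would instead need follow-up to month 48 on the implied schedule.
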